3.3.2 Laboratory data

Blood and urine samples for determination of clinical chemistry, hematology, and urinalysis will be taken at the times indicated in the assessment schedules and as clinically indicated Sections 1.1 and 8.2.1 of the CSP.

Change from baseline in hematology and clinical chemistry variables will be calculated for each post-dose visit on treatment. CTCAE grades will be defined at each visit according to the CTCAE grade criteria using local ranges as required, after conversion of lab result to corresponding preferred unit. The following parameters have NCI CTCAE grades defined for both high and low values: Hemoglobin, Leukocytes, Lymphocytes, Potassium, Sodium, Magnesium and Corrected calcium so high and low CTC grades will be calculated.

Absolute values will be compared to the local laboratory reference ranges and classified as low (below range), normal (within range or on limits of range) and high (above range).

The maximum or minimum on-treatment value (depending on the direction of an adverse effect) will be defined for each laboratory parameter as the maximum (or minimum) post-baseline value at any time.

Corrected calcium product will be derived during creation of the reporting database using the following formula:

$$\text{Corrected calcium (mmol/L)} = \text{Total calcium (mmol/L)} + ([40 - \text{albumin (G/L)}] \times 0.02)$$

Project reference ranges will be used for the primary interpretation of laboratory data. Local reference ranges will be used for analysing laboratory data at the local laboratory. The denominator used in laboratory summaries of CTCAE grades will only include evaluable patients, in other words those who had sufficient data to have the possibility of an abnormality.

For example:

- If a NCI CTCAE criterion involves a change from baseline, evaluable patients would have both a pre-dose and at least 1 post dose value recorded.
- If a NCI CTCAE criterion does not consider changes from baseline to be evaluable, the patient need only have 1 post dose value recorded.

3.3.3 ECG data

ECGs will be recorded at screening and as clinically indicated throughout the study (see Section 1.1 of the CSP).

3.3.4 Vital signs

Changes in vital signs variables between baseline and each subsequent scheduled visit will be calculated.

Body surface area (BSA) will be calculated from the height (in centimeters) and weight (in kilograms) as follows:

$$BSA = \sqrt{((\text{Weight (kg)} * \text{height(cm)}) / 3600)}$$

or (Du Bois formula)

$$BSA = 0.007184 \times W^{0.425} \times H^{0.725}$$

3.3.5 Exposure and dose intensity

Duration of exposure is defined as:

- Total treatment duration (in days) = min (date of last dose > 0mg + 27 days, date of death, date of DCO) - date of first dose + 1.
- Actual treatment duration = total treatment duration, excluding the duration of dose delays.

Exposure will be defined separately for durvalumab monotherapy, and for combination treatment.

For the combination therapy, date of first dose refers to first dose of tremelimumab and date of last dose refers to the latest last dose of either durvalumab or tremelimumab, when

durvalumab is not being received as monotherapy, and a dose delay is any day(s) when neither of these treatments was received.

If a patient has more than one period of combination therapy, or monotherapy, then each period will be summed when deriving the exposure to durvalumab monotherapy and combination treatment.

In addition, the total number of dosing occasions will be calculated per patient. The calculation of actual exposure makes no adjustment for any dose reductions that may have occurred.

The relative dose intensity (RDI) will be calculated for each patient for both durvalumab and tremelimumab. RDI is the percentage of the actual dose delivered relative to the intended dose through to treatment discontinuation. RDI will be defined as follows:

$RDI (\%) = d/D * 100$, where d is the actual cumulative dose delivered up to the actual last day of dosing and D is the intended cumulative dose up to the or the actual last day of dosing. D is the total dose that would be delivered if there were no modification to dose or schedule.

The actual cumulative dose (mg/kg) per patient in a time period is the sum of the actual dose levels that the patient received within that period (i.e. total dose administered mg/kg).

Treatment Delays

Delays will be derived based on infusion date and will be based on the deviation of the actual to the planned treatment administration day (relative to the previous treatment administration date). A delay is defined as more than 1 day of delay between the actual and the planned treatment administration day. For example, if one patient receives the study drug on day 1, then the next study drug administration date will be on day 29 (Day 1 of next cycle); however, if the patient receives the study drug at day 31 (Day 3 of next cycle), this is considered as a delay of 2 days. For all dosing dates, the total duration of dose delays = Sum of (date of the dose - date of the previous dose – 28 days). Thus, if no delays were encountered, the duration would sum up to 0, since infusions were done every 4 weeks.

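### SAP 3.3.5 gives two incompatible definitions of a dose delay for combination therapy and does not say which one governs actual combination duration

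*SAP*

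**What the plan says.** SAP 3.3.5 sets out exposure in steps.

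- Total duration: "Total treatment duration (in days) = min (date of last dose > 0mg + 27 days, date of death, date of DCO"), minus the date of first dose, plus 1.
- Actual duration: "Actual treatment duration = total treatment duration, excluding the duration of dose delays".
- Start of the combination period: "For the combination therapy, date of first dose refers to first dose of tremelimumab".
- Delay during the combination period: "a dose delay is any day(s) when neither of these treatments was received".

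Further down the same section, under Treatment Delays, delay is defined in another way. Delays "will be based on the deviation of the actual to the planned treatment administration day", taken relative to the previous administration. The threshold is then given: "A delay is defined as more than 1 day of delay between the actual and the planned treatment administration day". A worked example treats dosing on day 31 instead of day 29 as a delay of 2 days. The formula, which covers every infusion, reads: "the total duration of dose delays = Sum of (date of the dose - date of the previous dose – 28 days"). The SAP then states the result for an on-schedule patient: "if no delays were encountered, the duration would sum up to 0, since infusions were done every 4 weeks".

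SAP 4.2.3.7 plans summaries of total and actual duration for combination treatment and for durvalumab monotherapy, and of the number of patients with at least one delay. Protocol 9.5.2 also plans summaries of combination exposure and dose delays.

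**The concern.** The combination clause does not mention the planned day. It refers only to days on which neither drug was received, and on a four-weekly schedule that describes 27 of every 28 days for a patient who is never late. The Treatment Delays paragraph says that such a patient has no delay. The two statements cannot both define the quantity that is subtracted to give actual duration.

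At stake is whether one planned output can be reproduced. The combination clause is the only rule written specifically for two drugs, so a programmer could let the specific rule override the general one. A second programmer checking the output could use the Treatment Delays formula. Both would be following SAP 3.3.5, and their actual combination durations would differ by more than a hundred days per patient. Exposure is part of the context in which the toxicity of the combination is read.

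**Working it through.** **Inputs.** Four combination cycles of 28 days each (SAP 1.2). The duration formulas and both delay rules come from SAP 3.3.5. Days are counted from the first tremelimumab dose. I assume that both drugs are given on the same day and that neither death nor data cut-off truncates the period.

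**The SAP's own figures.** The Treatment Delays formula reproduces both.

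- Worked example, doses on days 1 and 31: 31 − 1 − 28 = 2 days, as stated.
- On-time dosing on days 1, 29, 57 and 85: (29 − 1 − 28) + (57 − 29 − 28) + (85 − 57 − 28) = 0, as stated.

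**On-time patient under each rule.**

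- Total duration = (85 + 27) − 1 + 1 = 112 days.
- Treatment Delays rule: delay 0, so actual = 112 − 0 = 112 days.
- Combination clause read literally: 4 infusion days, so delay = 112 − 4 = 108 and actual = 112 − 108 = 4 days (4/112 = 3.6%).

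**Patient with the second infusion 14 days late** (the longest delay between cycles that protocol 4.1.1 allows before a cycle is skipped). Infusions fall on days 1, 43, 71 and 99.

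- Total duration = (99 + 27) − 1 + 1 = 126 days.
- Treatment Delays rule: (43 − 1 − 28) + 0 + 0 = 14, so actual = 126 − 14 = 112 days.
- Combination clause read literally: delay = 126 − 4 = 122, so actual = 4 days.

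| Infusion days | Total | Delay / actual, Treatment Delays | Delay / actual, literal combination clause |
|---|---|---|---|
| 1, 31 (SAP example) | 58 | 2 / 56 | 56 / 2 |
| 1, 29, 57, 85 (on time) | 112 | 0 / 112 | 108 / 4 |
| 1, 43, 71, 99 (14 days late once) | 126 | 14 / 112 | 122 / 4 |

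In the last column the actual duration is simply the number of infusion days. It is the same with and without a 14-day delay, so it carries no information about delay.

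**The case against.** The strongest reply is that section 3.3.5 should be read as a whole. The term subtracted is the duration of dose delays. Treatment Delays defines that term by formula for all dosing dates, illustrates it, and states that on-time dosing gives 0. On that reading the combination clause only settles whose lateness counts when there are two drugs: time is delayed only if neither is being given. Because the literal reading cannot measure delay at all, it is unlikely to be what the authors meant.

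Most of this stands. It rules out two inferences that a reader might draw.

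- A reader might infer that the SAP assigns a fully compliant patient 4 days of actual combination exposure. It does not do so without qualification. That figure follows only from the combination clause taken by itself, and the same section says elsewhere that such a patient has no delay.
- A reader might infer that every patient would appear in the count of patients with at least one delay. The documents do not support that either. Treatment Delays states what counts as a delay, namely more than 1 day off the planned day, and an on-schedule patient does not meet it.

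The reply does not remove the conflict. The SAP never says that the general paragraph overrides the combination clause. Nor can the clause be set aside: Treatment Delays speaks of the study drug in general and gives no rule for two drugs given on different dates or for one drug withheld. The word 'neither' in the combination clause is the only text that covers those cases, so the clause needs correcting.

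**Conclusion.** SAP 3.3.5 is internally inconsistent on dose delays during combination therapy. For an on-time patient the two rules give 108 and 0 delay days, and actual durations of 4 and 112 of 112 days. The likely intent is the Treatment Delays rule, and a careful programmer may well choose it, but the SAP does not say so.

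The impact is low. Only the actual duration of combination exposure, a descriptive summary, depends on the clause. Total duration is computed from dates, and relative dose intensity is delivered over intended dose, so neither uses it. Objective response rate, dose-limiting toxicities and the cohort decisions are unaffected, and it would be wrong to read the point as bearing on them. The figures rest on same-day administration of both drugs, four cycles, and no truncation by death or data cut-off.

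**What to change.** Replace the combination clause in SAP 3.3.5 with wording such as: for combination therapy, a dose delay is the number of days beyond the planned administration day (28 days after the previous administration, as in Treatment Delays) on which neither durvalumab nor tremelimumab had been given. This keeps the two-drug rule and ties it to the schedule. It returns 0 days for the on-time patient, 2 for the SAP's example and 14 for the late patient above.

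Make the edit together with any correction to the Treatment Delays sum, because the new clause refers to that paragraph. The sum does not apply the paragraph's own threshold: a dose 1 day late adds 1 day although it is not a delay. It also lets early doses cancel late ones: doses on days 1, 33, 57 and 85 give 4 − 4 + 0 = 0 although one dose was 4 days late.

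The cost is one clause in the SAP and the matching line in the programming specification. No new data are needed.

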Radiological efficacy assessments ^u	X	On-study efficacy assessments occur every 8 weeks ± 1 week (always relative to the date of first dose), until radiological progression plus an additional regularly scheduled follow-up scan. This schedule MUST be followed regardless of any delays in dosing. For patients who achieve an objective response (CR, PR) or stable disease, and for whom the response is still evident at 12 months, subsequent tumor assessments are to occur every 16 weeks. Unscheduled assessments can be performed at any time during the study, as clinically indicated, based on signs and symptoms							8.1

Note: All assessments on treatment days are to be performed prior to infusion, unless otherwise indicated.

Note: Patients who restart combination therapy (having subsequently progressed on durvalumab monotherapy following the completion of 4 months of combination therapy) should complete the same assessments starting from Cycle 1 Day 1 of the dose-expansion phase, with the exception of PK, ADA, tumor biopsies, blood for CCI analysis, blood for CCI sequencing, and CCI.

^a Visit windows are relative to the first day of each cycle.

^b Written informed consent/assent and any locally required privacy act document authorization must be obtained prior to performing any protocol-specific procedures, including screening/baseline evaluations. If laboratory or imaging procedures were performed for alternate reasons prior to signing consent, these can be used for screening purposes with consent of the patient's parent(s)/legally authorized representative(s). However, all screening laboratory assessments must have been obtained within 28 days of Cycle 1 Day 1 and imaging/staging examination results must have been obtained within 21 days of Cycle 1 Day 1. The unique enrollment code will be obtained after ICF signature, through the IRT/RTSM.

^c Any clinically significant abnormalities detected require a confirmatory ECG result.

^d Tobacco use will be collected at the Investigator's discretion.

^e Serum or plasma clinical chemistry (including LFT monitoring) and hematology may be performed more frequently if clinically indicated.

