4.2.3.7 Exposure and compliance

Study treatment exposure data will be listed for each patient.

The total and actual duration of durvalumab monotherapy and combination treatment exposure will be summarized.

Number of patients with at least one delay (and reason for delay), the number of patients with no delay, the number of dosing occasions and the RDI will also be summarized.

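### The SAP's total dose delay is a signed sum that contradicts its own definition of a delay, so actual treatment duration can be wrong in either direction and can exceed total duration

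*SAP*

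**What the plan says.** SAP 3.3.5 (Exposure and dose intensity, with its Treatment Delays paragraph) contains these pieces:

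- Definition: "A delay is defined as more than 1 day of delay between the actual and the planned treatment administration day". The planned day is set from the previous administration.
- Example: a dose due on day 29 is given late, and "if the patient receives the study drug at day 31 (Day 3 of next cycle), this is considered as a delay of 2 days".
- Total: "For all dosing dates, the total duration of dose delays = Sum of (date of the dose - date of the previous dose – 28 days").
- Check on the total: "Thus, if no delays were encountered, the duration would sum up to 0, since infusions were done every 4 weeks".
- Durations: "Total treatment duration (in days) = min (date of last dose > 0mg + 27 days, date of death, date of DCO) - date of first dose + 1", and "Actual treatment duration = total treatment duration, excluding the duration of dose delays".

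The same section words a delay differently for combination therapy, as any day on which neither drug was received.

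SAP 4.2.3.7 lists the output: "The total and actual duration of durvalumab monotherapy and combination treatment exposure will be summarized". It also lists the numbers of patients with and without a delay, reasons for delay, dosing occasions and RDI.

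In Protocol 1.1, the headers of Tables 1 and 2 give a ±4-day window for Day 1 of Cycle 2 and of Cycle 3 onwards, and the footnote reads: "Visit windows are relative to the first day of each cycle". No minimum of 28 days between doses is stated in the documents.

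**The concern.** The definition and the formula measure different things. The definition looks at each dose, counts lateness only, and ignores 1 day. The formula is a signed sum with no floor at zero and no 1-day threshold. An interval shorter than 28 days is compatible with the protocol and subtracts from the total; an interval of 29 days is not a delay but adds to it.

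The protocol's dosing text (4.1.1, 6.1.1.1) rules out dose reductions and allows delays, and Protocol 9.5.2 commits to summarizing dose delays. Delay and actual exposure are therefore part of how tolerability is described. At stake is a table in which a patient counted as delayed contributes no delay days, or in which actual duration is longer than the total duration it is meant to be a part of.

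**Working it through.** **Inputs.** The formulas are those of SAP 3.3.5; the ±4-day windows are those of Protocol Tables 1 and 2. Dose days are d₁, …, d_k. Assume one continuous treatment period and no truncation by death or data cut-off.

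- Delay sum (SAP) = Σ(dᵢ - dᵢ₋₁ - 28)
- Total duration = d_k + 27 - d₁ + 1
- Actual duration = total - delay sum
- Delay by the SAP's own definition = sum of (interval - 28) over intervals where that difference exceeds 1

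**The SAP's own figures are reproduced.** Days 1, 31: sum 2, total 31 + 27 - 1 + 1 = 58, actual 56. Days 1, 29, 57, 85: sum 0, total and actual both 112.

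**Other dose dates**

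| Dose days | Interval - 28 | SAP sum | Total | SAP actual | Delay by definition | Actual by definition |
|---|---|---|---|---|---|---|
| 1, 25, 53, 81 | -4, 0, 0 | -4 | 108 | 112 | 0 | 108 |
| 1, 33, 57 | +4, -4 | 0 | 84 | 84 | 4 | 80 |
| 1, 25, 67 | -4, +14 | 10 | 94 | 84 | 14 | 80 |
| 1, 30, 59, 88 | +1, +1, +1 | 3 | 115 | 112 | 0 | 115 |

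Rows 1, 2 and 4 lie inside the ±4-day window whether it is read against the original 28-day calendar (nominal days 29, 57, 85) or against the previous dose. Row 3 adds a 14-day delay, the longest the protocol permits before a cycle is skipped.

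In row 1 actual exceeds total by 4 days (4/108 = 3.7%). In row 2 a real delay disappears. In row 3 a 14-day delay becomes 10 (4/14 = 29% too low). In row 4 the error runs the other way: 3 days of delay where the definition finds none.

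**Why this happens.** The sum telescopes:

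Σ(dᵢ - dᵢ₋₁ - 28) = (d_k - d₁) - 28(k - 1)

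Total duration is d_k - d₁ + 28, so

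actual = (d_k - d₁ + 28) - (d_k - d₁) + 28(k - 1) = 28k.

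Without truncation, actual duration is always 28 × number of doses, whenever those doses were given. It exceeds total duration whenever d_k - d₁ < 28(k - 1).

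**How far in-window timing alone can move the sum.** Read against the original calendar, the sum is the last dose's deviation from its nominal date, so it lies between -4 and +4. Read against the previous dose, it can reach 4(k - 1) in either direction, for example 12 days for k = 4.

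**The case against.** The strongest reply is that little depends on this quantity. SAP 4.2.3.7 does not list total delay duration as an output of its own, so the sum reaches the tables through actual duration. The count of patients with a delay can follow the per-dose definition, RDI is built from cumulative dose, and ORR does not involve delays. All of that stands and sets the scale of the point.

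A second reply is that 28 × number of doses is an interpretable measure of dose coverage, and that in the 1, 25, 67 case 10 days is the slip from the original calendar (day 67 against day 57). Both observations are correct. But the SAP measures a delay from the previous dose, which gives 14, and it describes actual duration as total duration with delays removed. The formula delivers neither. The number of dosing occasions is already summarized, so without truncation a duration equal to 28 times that number adds nothing.

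A reader might also infer that delays will be systematically understated and actual exposure overstated. The documents do not support that: early doses push the sum down and 1-day late shifts push it up, so the net direction depends on dates not yet seen. Nor do they show that any program already contains the error; only the SAP wording is available.

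**Conclusion.** The point holds as an internal contradiction in SAP 3.3.5. The delay formula does not implement the delay definition, and the statement that the sum is 0 when there are no delays is not true in general. Actual treatment duration can be too long or too short, and it can exceed total duration.

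In the cases worked above, the error in delay days is between 3 and 4 days per patient. These are constructed cases. How often intervals other than 28 days occur cannot be known from the documents, so no average effect can be given. The conclusion assumes that sites use the ±4-day window for dosing visits as printed. The identity with 28 × number of doses also requires no truncation by death or data cut-off.

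It would be a step too far to conclude that the tolerability assessment, RDI, the count of delayed patients or the primary ORR analysis is compromised. None of them uses this sum. The defect is confined to descriptive delay-duration and actual-exposure summaries, and is worth correcting because the correction is nearly free.

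**What to change.** In SAP 3.3.5:

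1. Define total delay as the sum of (interval - 28 days) only over intervals where that difference exceeds 1 day. No separate floor at zero is then needed.
2. Use this same quantity in actual treatment duration.
3. Replace the closing sentence: the sum is 0 when no interval meets the definition of a delay, whether or not infusions were exactly 4 weeks apart.
4. Reconcile the combination-therapy wording with this rule. It refers to days without either drug and is tied neither to a planned day nor to the 1-day threshold.

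The cost is a short SAP edit and the matching change in the derivation specification. It uses dosing dates that are already collected, needs no new data, and leaves every endpoint analysis as it is.

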3.3.6 Dose Limiting Toxicities (DLTs)

Dose-limiting toxicities will be determined during Cycles 1 and 2 of the dose-finding phase using CTCAE version 5. Toxicities that occur during the first 28-day cycle and meet the criteria below will be assessed for attribution to durvalumab monotherapy. Any of the below listed AEs encountered between Cycle 1 Day 1 and Cycle 2 Day 28 (ie, 56 day DLT monitoring period for combination therapy) and in the opinion of the Investigator is thought to

be attributable to durvalumab or/and tremelimumab, given a reasonable possibility based on temporal exposure to IP and for which an alternate etiology does not exist or cannot be identified, will be classified as DLTs:

- Grade 5 toxicity
- Hematological toxicity: Any Grade ≥ 3 (including febrile neutropenia Grade ≥ 3) except for the following:
 - Grade 3 thrombocytopenia that does not result in a bleeding event or does not require platelet transfusion
 - Grade 3 neutropenia that resolves to Grade ≤ 2 within 7 days.
- Non-hematological toxicity:
 - Any Grade 4 immune-related AE (irAE)
 - Any \geq Grade 3 colitis
 - Any Grade 3 or 4 noninfectious pneumonitis
 - Any Grade 2 pneumonitis that does not resolve within 5 days to \leq Grade 1 after initiation of maximal supportive care (including use of steroids)
 - Any Grade 3 irAE, excluding colitis or pneumonitis, that does not downgrade to Grade 2 within 3 days after onset of the event despite optimal medical management including systemic corticosteroids and does not downgrade to \leq Grade 1 or baseline within 14 days of onset
 - Liver transaminase elevation $>5 \times$ ULN or total bilirubin $>3 \times$ ULN. For patients with liver metastases at baseline, transaminase elevation $>8 \times$ ULN will constitute a DLT
 - Grade 4 vomiting, diarrhea, electrolyte abnormality, or systemic reaction
 - Grade 3 toxicity lasting >7 days despite optimal supportive care
 - Any \geq Grade 3 non-irAE, except for the exclusions listed below
 - Any Grade 3 immune-mediated peripheral neuropathy or other immune-mediated neurotoxicity
 - Grade ≥ 3 inflammatory reactions.

The definition of DLTs excludes the following conditions:

- Grade 3 fatigue lasting ≤ 7 days.
- Grade 3 endocrine disorder (pituitary and/or adrenal insufficiency) that is managed with or without systemic corticosteroid therapy and/or hormone replacement therapy and the patient is asymptomatic.
- Grade 4 hypothyroidism adequately treated with hormone replacement.
- Grade 3 inflammatory reaction attributed to a local antitumor response (eg, inflammatory reaction at sites of metastatic disease, lymph nodes, etc.).

- Concurrent vitiligo or alopecia of any AE grade.
- Grade 3 infusion-related reaction (first occurrence and in the absence of steroid prophylaxis) that resolves within 6 hours with appropriate clinical management.
- Grade 3 fever (fever greater than 40°F for ≤24h in duration).
- Any grade lymphopenia.
- Isolated Grade 3 electrolyte abnormalities that are not associated with clinical signs or symptoms and are reversed with appropriate maximal medical intervention (including supplementation) within 7 days of initiating supplementation.

irAEs are defined as AEs of immune nature (ie, inflammatory) in the absence of a clear alternative etiology. In the absence of clinical abnormality, repeat laboratory testing must be conducted to confirm significant laboratory findings prior to designation as a DLT.

Guiding principles:

1. While the rules outlined above dictate the classification of AEs as DLTs, any other AEs that are observed during the observation period may be defined as a DLT in consultation with the DRC; after having taken into consideration the emerging safety profile of durvalumab and tremelimumab.
2. The NCI CTCAE (version 5.0) will be used for AEs reporting and its severity will be graded on a scale from 1 to 5 provided for each AE term.
3. An immune-mediated AE is defined as an AE that is associated with exposure to durvalumab or/and tremelimumab and is consistent with an immune-mediated mechanism of action after alternate etiologies have been considered and excluded.
4. In the absence of clinical findings, repeat laboratory testing must be conducted to confirm the clinical significance of abnormal laboratory test result before it is classified as a DLT.

For reporting purposes, the DLTs are as approved and documented at the DRC meetings.

